### 12.3.1.2 IV to Oral Cohort

For the IV to oral cohort, duration of IV exposure (hours), duration of oral exposure (days), total duration of exposure (days), IV dose (mg), oral dose (mg), total dose (mg), mean daily IV dose (mg), mean daily oral dose (mg), and mean daily total dose (mg) will be summarized for the Safety set, calculated as follows:

Duration of IV Exposure =  $\sum t_v - \sum t_i$  where

 $t_v$  = all IV/infusion administration time intervals, calculated as end date/time – start date/time (hrs)

 $t_i$  = all IV/infusion interruption time intervals, calculated as stop date/time – start date/time (hrs). Note:  $\sum t_i$  = Total Duration of Interruptions

Duration of Oral Exposure = date of last oral exposure - date of first oral exposure + 1

Total Duration of Exposure = date of last exposure - date of first exposure + 1

IV Dose =  $\sum (t_v r_v c) - \sum (t_i r_i c)$  where:

 $t_v$  and  $t_i$  are as defined above (hr)

 $r_v$  = infusion rate (mL/h)

 $r_i$  = infusion rate at start of interruption

c = concentration (mg/mL) Note: Concentration for subjects treated with ganaxolone is cohortdependent. Concentration for placebo subjects is 0.

Oral Dose =  $\sum k_v c$  where:

 $k_v$  = number of capsules taken during the vth interval of oral dosing, where each interval is defined by a fixed number of capsules taken per day

c = concentration (mg) Note: Concentration for placebo subjects is 0.

Total Dose = IV dose + oral dose

Mean Daily IV Dose = IV Dose Days Exposed to IV Dose where:

Days Exposed to IV Dose = last end date of last IV/infusion- first start date of first IV/infusion + 1.

Mean Daily Oral Dose = Days Exposed to Oral Dose where:

Days Exposed to Oral Dose = date of last oral exposure – date of first oral exposure + 1.

Mean Daily Total Dose =  $\frac{\text{Total Dose}}{\text{Total Days Exposed}}$  where:

Total Days Exposed = date of last exposure – date of first exposure + 1.

Details of infusion interruptions and discontinuations will be listed.

Oral compliance will be summarized and will be calculated as:

100 x [Total Actual Oral Dose] Total Expected Oral Dose]

where Actual Oral Dose will be based on returned capsule count.

PRS 005 T 17 F

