#### 3.4.5 **Cohort 6**

For Cohort 6, the goal of initiation of treatment with IV infusion followed by oral capsules is to maximize the speed of onset of antidepressant activity while providing the convenience of oral dosing for the remainder of the treatment period. Under this IV-oral dosing schedule there may not be a need for a prolonged inpatient observation.

This initial infusion is targeted to provide a fast onset of antidepressant activity by delivery of rapid plasma exposures to ganaxolone. At dinner time of Day 1 the subjects will take their first oral dose of ganaxolone 900 mg or matching placebo (4 capsules). This dose is expected to provide mean  $C_{max}$  plasma concentrations of approximately 250-300 ng/mL and mean steady-state levels between 90 and 150 ng/mL, which may be mildly sedating. In previous studies ganaxolone has been given up to a daily dose of 2000 mg, and at single doses of 1000 mg. Based on the previous experience this dose is expected to be safe.

At subsequent nights (Days 2-28), the target dose is ganaxolone 900 mg or matching placebo (4 capsules) at dinner time followed by a 3-day taper (3, 2, and 1 capsule/s per day, respectively). However, based on the assessment of the investigator the dose may be maintained at 675 mg or 450 mg (or matching placebo) in case of adverse events, such as grogginess in the morning. In the case of 3 capsules per day on day 28 the taper will consist of 2, 2, and 1 capsule/s on days 29, 30, and 31, respectively. In the case of 2 capsules per day on day 28 the taper will consist of 1 capsule on days 29, 30, and 31. If the subject cannot tolerate 450 mg (or matching placebo) per dose the investigator will contact the Medical Monitor to discuss dosing options.

Subjects will be provided with a diary to capture the details of dose administration and associated food intake throughout the treatment period. Subjects will document the number of capsules taken and whether a fatty meal/snack (e.g., fatty yogurt, nuts, avocado) was consumed  $\pm 15$  minutes of taking the capsules.

The mechanism by which ganaxolone is postulated to be efficacious under this dosing regimen is restructuring of sleep architecture. Preclinical studies have shown that allopregnanolone has the capacity to modulate sleep, and disturbed sleep architecture is one of the hallmarks of depression.

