#### 6.1.3 Ganaxolone oral capsules

Ganaxolone capsules will be provided in size 00 white/opaque gelatin capsules packaged in HDPE bottles with a foil induction seal and child resistant closure. Each bottle will contain 70 capsules. Each capsule contains 225 mg ganaxolone ( $3\alpha$ -hydroxy- $3\beta$ -methyl- $5\alpha$ -pregnan-20-one), and hydroxypropyl methylcellulose, sucrose, polyethylene glycol 3350, polyethylene glycol 400, sodium lauryl sulfate, sodium benzoate, citric acid anhydrous, sodium methyl paraben, microcrystalline cellulose, 30% Simethicone Emulsion, gelatin capsules, polysorbate 80, and sodium chloride.

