# 9.0 Analysis Sets

The **Screened Set** will consist of all subjects who have signed an informed consent.

The Randomized Set will consist of all subjects who were randomized.

The **Safety Set** will consist of all subjects who received IP.

The **modified Intent to Treat Set** (mITT) will consist of all subjects in the Safety Set who have at least 1 post-randomization efficacy assessment.

The **Per Protocol (PP) Set** will consist of all subjects in the mITT set who do not have protocol deviations that may affect key efficacy endpoints.

The **Infusion Completer Set** will consist of all subjects in the IV only cohorts (cohorts 1-5) who completed the 60-hour infusion and all subjects in the IV to oral cohort (cohort 6) who completed the initial infusion.

The **Completer Set** will consist of all subjects in the IV only cohorts who completed the 60-hour infusion and attended all outpatient visits, and all subjects in the IV to oral cohort who completed the initial infusion and oral IP dosing period with at least 80% oral dosing compliance and attended all outpatient visits.

Subjects in the Safety Set will be analyzed according to the actual treatment received. Subjects in the Randomized, mITT, and both completer sets will be analyzed according to assigned treatment regardless of actual treatment received.

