# 12.1 Subject Disposition

The summary of subject disposition will include number and percentage of subjects in each analysis set, subject status at the end of the trial (completed or discontinued), and reason for discontinuation.

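### Followed as written, the SAP's oral compliance ratio for Cohort 6 has no usable value on placebo, and its expected dose is not defined

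*SAP*

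**What the plan says.** SAP 12.3.1.2 lists oral dose, in mg, among the Cohort 6 exposure measures. It is the sum of k_v times c, where k_v is the "number of capsules taken during the vth interval of oral dosing, where each interval is defined by a fixed number of capsules taken per day" and c is the "concentration (mg) Note: Concentration for placebo subjects is 0".

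At the end of the same section, oral compliance is to be summarized as 100 times the total actual oral dose over the "Total Expected Oral Dose". The only further instruction is "where Actual Oral Dose will be based on returned capsule count". No unit is given for the ratio. Neither the SAP nor the protocol defines the expected dose.

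SAP 9.0 uses this percentage as a membership rule. The Cohort 6 Completer Set needs a completed infusion and a completed "oral IP dosing period with at least 80% oral dosing compliance and attended all outpatient visits"; Protocol 9.5.3 carries the same 80% threshold. SAP 12.1 says that the disposition summary "will include number and percentage of subjects in each analysis set", and SAP 12.0 presents tables by treatment group within cohort.

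Protocol 3.4.5 allows reductions: "the dose may be maintained at 675 mg or 450 mg (or matching placebo) in case of adverse events". It gives a separate taper for each reduced level. Protocol 6.2.4 repeats the permission and requires the adjustment to be recorded in the eCRF.

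**The concern.** There are two separate gaps.

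The first is the unit. Setting c to zero on placebo is right for an exposure table, because those women receive no ganaxolone. It does not work in a measure of whether capsules were taken. The compliance ratio reuses the oral dose term without redefining it, so the zero carries over.

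The second is the denominator. A woman whose dose is lowered under the protocol can take every prescribed capsule and still look non-adherent, if she is measured against the full 900 mg schedule.

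At stake are the compliance summary and the Completer Set count in the disposition table, both of which are meant to be read side by side by arm.

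**Working it through.** The documents state no compliance figure, so there is nothing to reproduce. The check applies the SAP formulas to women who take every capsule.

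**Inputs**
- Capsule strength: "Each capsule contains 225 mg ganaxolone" (Protocol 6.1.3), so 4, 3 and 2 capsules are 900, 675 and 450 mg.
- Target regimen: 4 capsules a day for 28 days, then 3, 2, 1 (SAP 6.1).
- Taper after 3 capsules a day: 2, 2, 1. Taper after 2 a day: 1, 1, 1 (Protocol 3.4.5).
- Threshold: 80% (SAP 9.0).

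**Full schedule**
- With taper: 28 × 4 + 6 = 118 capsules = 118 × 225 = 26,550 mg. The 80% line is 0.8 × 118 = 94.4 capsules.
- Without taper: 28 × 4 = 112 capsules. The 80% line is 89.6.

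**Placebo, full adherence**
- c = 0 in numerator and denominator: 0/0, undefined.
- c = 0 in the numerator, 225 mg in the denominator: 0/26,550 = 0%.
- Capsules in both: 118/118 = 100%.

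**Dose-reduced, full adherence, denominator fixed at the 900 mg schedule**

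Let d be the number of days at 4 capsules before the reduction. Day 1 is a full-dose day, so a reduction from Day 2 is d = 1.
- To 3 capsules, with taper: 4d + 3(28 − d) + 5 = 89 + d. At d = 1, 90/118 = 76.3%. At d = 5, 94/118 = 79.7% (below 80%). At d = 6, 95/118 = 80.5% (passes).
- To 2 capsules, with taper: 4d + 2(28 − d) + 3 = 59 + 2d. At d = 1, 61/118 = 51.7%. At d = 17, 93/118 = 78.8% (below). At d = 18, 95/118 = 80.5% (passes).
- To 3 capsules, taper not counted: 84 + d. At d = 5, 89/112 = 79.5% (below). At d = 6, 90/112 = 80.4% (passes).
- To 2 capsules, taper not counted: 56 + 2d. At d = 16, 88/112 = 78.6% (below). At d = 17, 90/112 = 80.4% (passes).

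**Dose-reduced, full adherence, denominator = prescribed regimen**
- Reduced from Day 2: 90/90 and 61/61, both 100%. The same holds for any reduction day.

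So the undefined denominator alone decides whether these women count as completers.

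**The case against.** The best defence is that the zero for placebo sits under the exposure formula. Compliance comes later as its own item, with its own data source, returned capsules. A capsule ratio is well defined on placebo, and a sensible programmer would use it. A whole arm at 0% or missing would also be obvious once tables were run; SAP 11.2 describes data screening through table programming. Much of this stands: the intended calculation is probably the capsule one, and a silent error is unlikely. But the returned-count sentence says where the count comes from. It neither replaces the mg definition nor sets a new unit, so the SAP does not instruct the version that works.

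On reductions, a reader might infer that adherent dose-reduced women will be marked non-compliant. The documents do not support that. The expected dose is left open, and the level-specific tapers and the eCRF record of adjustments would allow a prescribed-regimen denominator. Even on the 900 mg reading, only the earlier reductions fail.

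A reader might also infer that reductions make the Completer Set wrong by arm. Protocol 1.2.1.1 gives somnolence as 22.0% on ganaxolone and 6.4% on placebo in completed placebo-controlled studies, and Protocol 6.2.4 names sedation as a reason to lower the dose, so the direction is plausible. But reductions are allowed in both arms and neither document gives a reduction rate, so an imbalance is not established.

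**Conclusion.** The point holds as a specification defect of minor severity.

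For placebo, the SAP's own definition yields 0/0 or 0% for every woman in the arm. None could meet the 80% rule, and the arm's compliance summary and Completer Set count would be invalid. This rests on carrying the mg definition of oral dose into the compliance ratio, which is what the text says.

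For dose-reduced women the finding is conditional. Only if the expected dose is the 900 mg schedule do adherent women fall below 80%: after 5 or fewer full-dose days for 675 mg (taper counted or not), and after 17 or fewer for 450 mg (16 or fewer if the taper is not counted).

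It would go too far to read this as a threat to the trial's results. Efficacy is analysed primarily in the mITT set (SAP 12.5) and safety in the Safety Set (SAP 12.6). The Per Protocol Set has no 80% rule, and no table or figure in SAP Appendix 3 takes the Completer Set as its population. The set appears only as a count in the disposition summary and in the analysis-set listing.

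**What to change.** In SAP 12.3.1.2, define oral compliance in capsules for both arms:

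100 × capsules taken / capsules prescribed

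- Capsules taken: dispensed minus returned, plus the Day 1 dose given in the unit, which precedes the first bottle dispensed on Day 2 (Protocol 7.5.2 and 7.5.3).
- Capsules prescribed: the sum over days of the dose level in force, including the taper that belongs to that level.
- Early stopping: state whether the prescribed count ends at the stopping date or runs to the end of the schedule.
- Milligrams, with placebo at 0: keep for the exposure tables only.

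Under this rule the fully adherent cases above give 118/118, 90/90 and 61/61, all 100% in either arm. The cost is a few lines in the SAP and the matching program specification. No new data are needed: dispensing, return and accountability are already scheduled (Protocol 7.6.3 to 7.7.1), and dose adjustments already go into the eCRF (Protocol 6.2.4).

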#### **12.3.2 Concomitant Medications**

A concomitant medication is defined as any medication taken between the screening visit and the end of the follow-up period (i.e., the end date is on or after the screening visit date, or the subject is still taking the medication at the end of the follow-up period) regardless of the start date of the medication. Medications recorded with insufficient exposure dates to determine whether or not they were concomitant will be considered concomitant.

Concomitant medications will be categorized by preferred term according to WHO (World Health Organization) Drug Dictionary (Version 01DEC2017 Drug Dictionary Enhanced (DDE)) and will be summarized for the Safety Set. The number and percentage of subjects using each medication will be displayed for each preferred term.

### 12.4 Demographic and Baseline Characteristics

#### **12.4.1 Demographics**

The following demographic and other baseline characteristics will be summarized for the Safety Set:

- Sex (female)
- Age (years)
- Race (White, Black or African American, Asian, American Indian or Alaska Native, Native Hawaiian or Other Pacific Islander, Other)
- Ethnicity (Hispanic or Latino, Not Hispanic or Latino)
- Weight (kg)
- Height (cm)
- Body mass index (kg/m^2)

#### 12.4.2 Medical History

Medical history will be tabulated for the Safety Set by System Organ Class (SOC) and Preferred Term (PT) according to MedDRA Version 20.0.

#### **12.4.3 Prior Medications**

Prior medications are defined as medications with an end date prior to the screening visit date. If a partial date allows a medication to be considered a prior medication, it will be categorized as such.

Prior medications will be categorized by preferred term according to WHO Drug Dictionary (Version 01DEC2017 DDE) and will be summarized for the Safety Set. The number and percentage of subjects using each medication will be displayed for each preferred term.

#### 12.4.4 Mini International Neuropsychiatric Interview 7.0

The Mini International Neuropsychiatric Interview (MINI) is a short, clinician-administered, structured diagnostic interview, with an administration time of approximately 15 minutes conducted only at the screening visit. MINI data will not be summarized but will be presented in a data listing.

#### 12.4.5 SAFER Interview

Staff psychiatrists or psychologist at the Massachusetts General Hospital Clinical Trials Network and Institute will perform independent remote SAFER interview (State versus trait; Assessability; Face validity; Ecological Validity; and Rule of 3 Ps (pervasive, persistent, and pathological)) for the screened patients

PRS 005 T 17 F

who are deemed eligible for randomization to confirm validity of the diagnosis of PPD and eligibility for the study from depression perspective.

Time of SAFER interview and whether a subject is eligible based on inclusion criteria will be listed.

#### **12.4.6 Clinical Global Impression – Severity Scale**

The Clinical Global Impression – Severity scale (CGI-S) is a 7-point scale that asks the clinician to rate the severity of the subject's depression at the time of assessment, relative to the clinician's past experience with subjects who have the same diagnosis. Considering total clinical experience, a subject is assessed on severity of depression at the time of rating 1, normal, not at all ill; 2, borderline mentally ill; 3, mildly ill; 4, moderately ill; 5, markedly ill; 6, severely ill; or 7, extremely ill.

CGI-S responses will be assessed at Screening and Day 1 before infusion (Baseline) and will be summarized.

### 12.5 Efficacy Analyses

Statistical analysis of efficacy endpoints will primarily be done using the mITT set and will be done only to aid in interpretation as the trial was not powered for inferential hypothesis testing. As such, there will be no adjustments for inflation of type 1 error due to multiplicity.

For efficacy endpoints expressed as continuous variables, summary tables will show continuous summary statistics for each time point of data collection (visit) as well as least squares (LS) means with standard errors (SEs) and associated p-values from mixed model repeated measures (MMRM) analysis. Summary statistics by time point will also be displayed graphically using bar and/or line charts. MMRM models will include fixed effects for treatment, visit, and the treatment-by-visit interaction, and the baseline observation will be included as a covariate. Repeated measurements are made on each subject. Residuals will be evaluated for substantial departure from normality and independent and constant variance. Methods such as data transformation, detecting and assessing the influence of outliers, and alternative analytical approaches (e.g., non-parametric) may be used to address assumption deviations. An unstructured covariance will be the default covariance structure but other structures (e.g., compound symmetry) may be used to evaluate sensitivity to the choice of structure or, if necessary, to achieve convergence. MMRM assumes missing observations are missing at random (MAR); i.e., missingness depends only on variables other than the outcome that are available in the database. Because the MAR assumption is not testable, and because it seems possible that subjects with poorer outcome may be more likely to miss trial assessments, a sensitivity analysis may be done in which all missing data will be imputed. Conservatively, multiple imputation with a pattern-mixture model will be used; specifically, for all subjects with missing observations regardless of treatment assignment, imputation will be based only on subjects randomized to placebo. The imputation method will be fully conditional specification (FCS) regression with 25 imputations. Variables in the imputer's model will be observed values at each time point included in the MMRM analysis, including baseline.

For efficacy endpoints expressed as categorical (including binary) variables, summary tables will show frequencies and percentages of subjects in each category as well as adjusted event rates with SEs and associated p-values using general estimating equations (GEE). Summary statistics by time point will also be displayed graphically using bar charts. GEE models will include main effects for treatment and visit and an interaction term for treatment-by-visit. Baseline will be included as a covariate where applicable. Unstructured covariance will be specified but alternative structures (e.g., CS) or alternative statistical methods (e.g., chi square tests of association) may be used if GEE convergence cannot be achieved. GEE assumes missing observations are missing completely at random (MCAR); i.e., missingness is independent of all other information whether it was collected or not. A sensitivity analysis based on multiple imputation, as described above, may be done in which FCS logistic regression would be the imputation method.

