#### 12.5.1 Primary Efficacy Endpoint

The primary efficacy endpoint will be HAMD17 total score change from baseline to 60 hours post-infusion (on Day 3) for the IV only cohorts and to Day 29 for the IV to Oral cohort. Although the trial is not powered for inferential analysis and there is no consideration for control of type 1 error across multiple cohorts, a clinically meaningful numeric difference in means of 3-4 points between ganaxalone and placebo treatment groups would be considered an indication of efficacy and will be the most influential outcome in the overall assessment of the efficacy of ganaxalone in treating PPD.

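### SAP 12.5 checks MMRM residuals for independence and constant variance, which the default unstructured model does not assume across visits, and does not say that the original-scale MMRM stays the main analysis

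*SAP*

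**What the plan says.** SAP 12.5 defines the model for continuous efficacy endpoints: "MMRM models will include fixed effects for treatment, visit, and the treatment-by-visit interaction, and the baseline observation will be included as a covariate". It then notes: "Repeated measurements are made on each subject". The next sentence sets the diagnostic: "Residuals will be evaluated for substantial departure from normality and independent and constant variance". The consequence follows directly: "Methods such as data transformation, detecting and assessing the influence of outliers, and alternative analytical approaches (e.g., non-parametric) may be used to address assumption deviations". Only after that does the section name the covariance: "An unstructured covariance will be the default covariance structure but other structures (e.g., compound symmetry) may be used to evaluate sensitivity". A simpler structure is also allowed if the model does not converge.

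SAP 12.5.1 gives the criterion by which efficacy will mainly be judged: "a clinically meaningful numeric difference in means of 3-4 points between ganaxalone and placebo treatment groups would be considered an indication of efficacy".

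Three other places bear on this:

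- SAP 4.0 says that the SAP takes precedence over the protocol's statistical text. It asks for significant departures from the plan to be identified in the study report, and it needs no SAP update for changes made after database lock.
- Protocol 9.5.8.4 prefers MMRM but allows t-tests, ANCOVA or non-parametric methods on grounds of need or practicality.
- SAP 6.2 and 12.5 state that there is no formal hypothesis testing and no type I error adjustment.

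**The concern.** The diagnostic belongs to a different model. Independent residuals with one common variance are the assumptions of an ordinary regression that ignores who each rating came from. The planned MMRM is chosen because ratings from one woman are correlated and may vary more at some visits than others. Finding those features in raw residuals says nothing against it, yet the SAP would class them as assumption deviations.

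That classification matters because, for continuous endpoints, it is the SAP's main stated route from the MMRM to another method; the convergence clause changes only the covariance structure. Residuals from a model with treatment and treatment-by-visit terms can be computed only with treatment codes, so any change of method would be considered when results by arm can be seen. A rank-based or transformed analysis does not directly give a difference in HAMD17 points, which is the scale of the 3-4 point criterion. If the alternative were a single-visit test, it would also leave out women with no rating at +60h or Day 29, whom the MMRM keeps through their other visits. Protocol 2.1 says that the study results will be used to choose a dose and regimen for further development, so the estimate read against 3-4 points has a use even in an exploratory trial.

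**Working it through.** The plan gives no figure to reproduce: no test, significance level, threshold or residual type for the check.

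**What each model assumes.** For k post-baseline visits, the unstructured model gives a woman's errors a covariance matrix with k(k+1)/2 free parameters: k variances and k(k-1)/2 covariances. The reference in the residual sentence is that matrix set to one variance times the identity, which has one parameter.

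- Cohorts 1-5: HAMD17 at +12h, +24h, +48h, +60h, +72h, Day 11 and Day 34 (SAP 6.1, Table 1), so k = 7 and 7 × 8 / 2 = 28 parameters.
- Cohort 6: Day 1 at +6h, then Days 2, 4, 8, 11, 15, 22, 29, 36, 57 and 71 (SAP 6.1, Table 2), so k = 11 and 11 × 12 / 2 = 66 parameters.
- Women per cohort: about 10-30, allocated 1:1 (SAP 6.1).

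**How often a correct model would be flagged on raw residuals.** Data were simulated so that the planned MMRM is exactly right: normal errors, arm-by-visit means, a baseline covariate and complete data, with 300 runs per setting (Monte Carlo standard error at most √(0.25/300) = 2.9 percentage points). Two checks were applied, each at 5%: Levene's test across visits for constant variance, and the pooled lag-1 within-woman correlation for independence. The correlation, the ratio of last-visit to first-visit SD, and the 5% level are assumptions; the documents give none of them. Correlation was AR(1), with compound symmetry added at 0.3. With 10 women the residuals are from ordinary least squares, because the unstructured matrix cannot be fitted reliably.

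Share of runs with at least one flag:

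| Visits, women | corr. 0 | corr. 0.3 | corr. 0.5 | corr. 0.7 |
|---|---|---|---|---|
| 7, 10 | 13% | 54-55% | 93-94% | 99.7-100% |
| 7, 20 | 12% | 82-88% | 100% | 100% |
| 7, 30 | 8% | 94-97% | 100% | 100% |
| 11, 20 | 9% | 93-99% | 100% | 100% |
| 11, 30 | 12% | 99-100% | 100% | 100% |

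Two independent 5% checks would give 1 - 0.95² = 9.75%, so the first column is close to what is expected when the reference model is true. The rest is driven by the independence check. Levene's test alone flags 1-7% with equal SDs, 6-39% at an SD ratio of 1.5, 24-80% at 2 and 47-100% at 3.

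**On scaled residuals.** Let R be the residual matrix and LL' the fitted covariance, roughly R'R divided by its degrees of freedom. The scaled residuals R(L')⁻¹ then have a cross-product proportional to the identity, so correlation and unequal variance are removed almost by construction. In the setting run (AR(1) 0.7, SD ratio 2; 20 or 30 women; 7 or 11 visits) both checks flagged 0%. For these two features the check on scaled residuals shows almost nothing.

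**Effect on type I error.** A separate simulation had no treatment effect and 1,500 trials per setting. It used 6-15 women per arm with 7 visits or 10-15 per arm with 11 visits, correlation 0.5 exchangeable or 0.7 AR(1), and SD constant at 8 or rising from 5 to 9. Taking the smallest p-value of a t-test, a log-shifted t-test and a rank-sum test gave 0.051-0.069, against 0.043-0.058 for the t-test alone. The Monte Carlo standard error near 0.05 is √(0.05 × 0.95/1500) = 0.006.

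**The case against.** The case on the other side is substantial.

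- **No test is prescribed.** A reader might infer that the SAP applies a test that rejects a correct model nearly every time. It does not: it calls for a judgement of substantial departure, with no rule. The high flag rates need raw residuals, formal 5% checks and a correlation of about 0.5 or more (or 0.3 with larger cohorts or more visits). This stands in full, and no flag rate follows from the documents.
- **The authors clearly expect correlation.** The sentence on repeated measurements comes just before the check, and the unstructured default soon after. They may have meant independence between women and equal variance between arms. Those are real assumptions, since no arm-specific covariance is planned. The text does not say so, but a replacement should keep the between-arm check.
- **Nothing is forced.** A reader might infer that the MMRM will be replaced. The wording is permissive, includes outlier assessment, and never says the MMRM is withdrawn. Protocol 9.5.8.4 allows other methods with no residual finding at all. This stands, but the SAP takes precedence over the protocol. Because the SAP itself permits the alternatives, the disclosure rule in SAP 4.0 might not mark their use as a departure.
- **The point scale is not lost.** SAP 12.5 commits to summary statistics and least squares means by visit, and Appendix 3 lists observed values and changes in HAMD17. A difference in points will always be available. This also stands. What is unsettled is which estimate is read against 3-4 points if an alternative is run.
- **Low stakes.** Efficacy is hypothesis-generating and no alpha is controlled. That limits the severity, but it also makes the numeric criterion the working decision rule.

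**Conclusion.** The point holds as a mismatch in wording with a gap behind it. Under the default unstructured covariance, independence and constant variance across a woman's visits are not assumptions, so they should not be listed as grounds for an assumption deviation. On raw residuals the check would often mislead, and usually so at a correlation of about 0.5 or more under formal 5% checks; on scaled residuals it says almost nothing. The gap is that the SAP does not state that the original-scale MMRM remains the main analysis when a transformed or non-parametric one is used.

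The size is modest. The change in type I error is small (0.051-0.069 against 0.043-0.058 in the settings simulated), the tables in HAMD17 points remain planned, and no hypothesis is formally tested. A reader might infer serious false-positive inflation or a planned abandonment of the MMRM; neither the figures nor the text supports that. The simulated rates rest on assumed correlations, SD ratios, normal errors and complete data. The mismatch itself rests on none of these. One qualification applies: if compound symmetry is used to reach convergence, which is plausible with 28 or 66 parameters and 10-30 women, equal variance across visits becomes a real assumption, while independence within a woman still does not.

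**What to change.** Replace the residual sentence and the one after it in SAP 12.5 with:

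> Residuals scaled by the fitted covariance will be examined for normality and influential outliers, and residual spread will be compared between arms. Within-subject correlation, and unequal variance across visits when the unstructured covariance is used, are modelled and are not assumption deviations; if a structure with equal variances (e.g., compound symmetry) is used for convergence, variance across visits will be examined. The MMRM difference on the original HAMD17 scale is the estimate read against the 3-4 point criterion; transformed or non-parametric analyses are reported beside it as sensitivity analyses and do not replace it.

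The cost is a few sentences in the SAP and one output option in the SAS procedure (for example VCIRY in PROC MIXED) for the scaled residuals. It needs no new data and no change to the model. The downside is that the sponsor gives up the freedom to replace the MMRM after seeing residuals; every alternative remains available as a sensitivity analysis.
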